MRV-CCD (Malezi radio + radio + CCD program)	30%	45%	15%	80%	102	118
	50%	65%			106	123
	70%	85%			78	90

*STATA 14 paired proportions large-sample McNemar's test at 5% level significance.

Selection Criteria for Study Communities

The study will be implemented in probability selected geographic areas of the catchment villages surrounding selected health facilities in four districts of Tabora region. The health facilities will be purposefully selected, including the district hospital in each of the four districts. Each primary health facility has clearly designated villages assigned to that facility (about 3-7), and each village has recognized boundaries, administrative units and census enumeration areas (EA), defined by the National Bureau of Statistics (NBS). Further details on sampling EA units are described later in this protocol. District hospitals do not have village catchments because they are secondary level facilities, but up to about 7 villages immediately surrounding the district hospital will be included in the sampling frame.

All facilities will meet the following eligibility criteria at baseline:

1. Accessible by road in all seasons
2. Has at least 3 CHWs and sufficient health provider staff to maintain MNCH/PMTCT clinic as expected (2-5 days per week)

The MRV-CCD and MR communities each have additional recruitment criteria.

MRV-CCD catchment communities should also:

- Be located in Nzega or Igunga districts
 - Exclusion: Malezi CCD-program supported facilities in Tabora Municipal, because there are no comparably urban facilities in non-Malezi districts.

MR facility catchment communities should also:

- Be located in Kaliua or Uyui
- Have new antenatal care attendees in the past year comparable to facilities in MRV-CCD communities (within about 25% variance).

Given the small cluster size, it was not possible to randomly allocate sites to intervention groups.

Sampling within Study Communities

Study communities are defined as the villages within the catchment area of the selected health facilities (n~30). The NBS EA census maps, estimating the total number of households in that EA as of the last census (2012) will constitute the sampling frame. The sampling unit will be the EA, and the sampling approach will use probability proportional to size (PPS). This will result in the final selection of EAs being statistically representative of the total population within selected study communities of each study district.

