EAs average about 50 households, and do not overlap with other recognized administrative units (ward, village, hamlet, street), but their area and population size could vary from 20-100 households, and household size varies as well. The most recent census showed 19% of rural households had children under 5 years, and that Tabora averaged six persons per household. Since this evaluation targets caregivers of children 0-24 months of age at the time of recruitment, that means that an estimated 7.6% of households would be considered eligible ($[19/5]*2$). Thus a sample of about 250-300 EAs will be selected, using the estimate of 8% of households being eligible. Then, recruitment rates will be monitored to know whether additional EAs will be needed or not. In case they are needed, a second sampling also using PPS will be done, and all households in the second-sample EAs will be visited. In case too many EAs are sampled, and our expected sample size would be far exceeded by including all sample EAs, targets by ward will be calculated (proportional to expected sample size), and once the target has been reached within a ward, no additional EAs will be included for that ward. However, once an EA is “opened,” all households in that EA should be enumerated, even if the target is then exceeded for that ward.

Recruitment into the Caregiver Cohort

Recruitment into the caregiver cohort will take place in two stages, whereby potentially eligible caregivers are identified through household enumeration, screened for study eligibility, and invited to verbally consent to participate in the listenership survey (stage I). On another day during the baseline data collection period, all eligible and participating caregivers will be revisited for re-screening, informed consent, enrolment into the caregiver cohort, and full baseline survey administration (stage II). We expect less than 5% loss between recruitment into in stage I

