(listenership) and stage II (caregiver cohort). However, based on study methodology for complete enumeration of every “opened” enumeration area, it is possible that we will complete more than the expected number of listenership surveys in some wards. Where the number of listenership surveys completed is more than 10% greater than the ward’s target for cohort enrollment, selection of listenership participants for caregiver recruitment in that ward will be made using systematic random sampling. Those who participate in stage I only at baseline but are not selected for recruitment into the caregiver cohort, will not be continued in the study, and will therefore not be revisited for the endline listenership survey.

Data collectors with at least secondary or higher education, and trained in enumeration, eligibility determination, verbal consent and listenership survey administration will conduct stage I study procedures. Research Associates (RAs) with at least post-secondary or higher education, and trained in eligibility determination, written consent procedures, and the full caregiver survey will conduct stage II study procedures.

Stage I: Enumeration of households and caregiver listenership survey

Data collectors (enumerators) will be escorted by local leaders to facilitate community entry, complete listing within the EA boundary, and household introductions. All households within the selected EAs will be enumerated and classified as an eligible household for study recruitment if at least one caregiver of a child 0-24 months of age at the time of the enumeration visit resides in that household with the child.

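### Drawing EAs with probability proportional to size and then taking every eligible household over-represents large EAs, so the draw does not by itself give the representativeness the protocol states

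*Protocol*

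**What the plan says.** Under Sampling within Study Communities, the EA is the sampling unit and is selected by PPS. The size measure is the census map count, "estimating the total number of households in that EA as of the last census (2012) will constitute the sampling frame". The protocol then states: "This will result in the final selection of EAs being statistically representative of the total population within selected study communities".

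On EA size it says "EAs average about 50 households" and "their area and population size could vary from 20-100 households". It plans about 250-300 EAs, assuming 8% of households are eligible.

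There is no fixed take per EA. Once an EA is opened, "all households in that EA should be enumerated, even if the target is then exceeded for that ward". A second PPS draw, if needed, is also take-all. Study Population allows one caregiver per household.

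Two further rules are conditional. If too many EAs were drawn, targets are set by ward, and "once the target has been reached within a ward, no additional EAs will be included for that ward". Under Recruitment into the Caregiver Cohort, if completed listenership surveys exceed a ward's cohort target by more than 10%, "selection of listenership participants for caregiver recruitment in that ward will be made using systematic random sampling".

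**The concern.** The protocol credits representativeness to the PPS draw itself. That property belongs to PPS followed by a fixed number of households per EA. With take-all, a large EA counts twice: it is more likely to be drawn, and it contributes more households once drawn.

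The estimates exposed are descriptive ones made on caregivers. The first item under Research Questions is how far the radio messaging reaches caregivers of young children, and Data Analysis plans percentages and confidence intervals for listenership, perceptions, knowledge and practices. If reach or practices differ between small and large EAs, unweighted percentages do not describe the population named in the sampling section.

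The ward-closing rule adds a second problem. The protocol does not say in what order a ward's drawn EAs are opened, so which ones are left out when the target is met may depend on field order and on yields elsewhere in the ward. An analysis plan cannot recover those probabilities later if the order was neither randomised nor recorded.

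**Working it through.** **Inputs from the protocol.** Mean EA size about 50; range 20-100; eligible share 8% (7.6% before rounding); cohort 1214; all households taken in each opened EA.

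**Inputs assumed.** The protocol gives no distribution of EA sizes. I used a normal distribution centred at 50 with nominal SD 10, 15 or 20, truncated to 20-100. Truncation gives actual means of 50.0, 50.7 and 52.3 and SDs of 9.9, 14.1 and 17.2.

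**The plan's own figure.** EAs needed = 1214 / (households per EA × eligible share). At 50 households, 1214 / (50 × 0.08) = 303.5, or 319.5 at 7.6%. PPS selects larger EAs on average, with mean = mean size × (1 + CV²), here 52.0, 54.7 and 58.0. The need is then 1214 / (0.08 × that mean) = 292, 278 and 262 EAs. The stated 250-300 is therefore reproduced, and only under take-all.

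**Inclusion probability.** Let M be the household count of an EA and n the number of EAs drawn.
- PPS with fixed take b: (n·M/ΣM) × (b/M) = n·b/ΣM, constant.
- PPS with take-all: (n·M/ΣM) × 1, proportional to M.

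Over the stated range the ratio is 100/20 = 5. This needs no distributional assumption, but it compares the two extremes. It would be smaller, about 3.4, if the frame were so small (400 EAs assumed) that the largest EAs were drawn with certainty.

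**Effect on sample composition.** If EA sizes have density f(s), population households are distributed as s·f(s) and sampled households as s²·f(s).

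| Nominal SD | EAs over 60: population | EAs over 60: sample | Mean EA size per household: population → sample | Bias (points) | Kish factor 1 + CV² |
|---|---|---|---|---|---|
| 10 | 19% | 24% | 52.0 → 53.9 | 0.5 | 1.04 |
| 15 | 34% | 43% | 54.7 → 58.3 | 0.9 | 1.08 |
| 20 | 44% | 56% | 58.0 → 63.0 | 1.3 | 1.11 |

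The bias column assumes an outcome rising linearly from 20% in EAs of 20 households to 40% in EAs of 100, that is 20/80 = 0.25 points per household. For SD 20: (63.0 − 58.0) × 0.25 = 1.25. The gradient is an illustration; nothing in the protocol supports a particular value.

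**Ward rules.** Systematic subsampling has a known fraction, so it can be weighted. It comes after the baseline listenership survey, so it affects the cohort and endline estimates but not baseline listenership. Ward closing acts earlier, on which EAs are opened at all, and its probabilities are known only if the opening order is fixed by chance and recorded.

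**The case against.** **Narrow reading.** The sentence is about the selection of EAs, and under PPS an unweighted average of EA means is self-weighting for households. That is true, but the sentence claims to represent the total population, and Data Analysis works on caregivers, not EA means.

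**Weights may be in the analysis plan.** That plan is not at hand, so the absence of weights from the protocol is not the fault. The EA stage is a probability draw on known counts and can be weighted. What stands is the wrong attribution in the protocol, and the opening order, which has to be fixed in the field.

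**The effect is small.** At n = 607, 30% prevalence and the planned design effect of 1.2, the standard error is √(0.3 × 0.7 × 1.2 / 607) = 2.0 points, more than the illustrated bias. This is fair and keeps the point modest, though a larger sample would not remove the bias.

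**Stronger readings to avoid.**
- A reader might infer that the arm comparison is invalid. The DID and the within-arm change are contrasts, and much of a level shift cancels if EA-size distributions are similar across arms. Facilities are also purposefully selected, so the target population is already limited.
- A reader might infer that EAs will be opened by convenience. The protocol is silent on order; it does not say that. The closing rule applies only if too many EAs were drawn, and its targets are proportional to expected sample size.
- A reader might spread EA sizes evenly over 20-100 and find 66% of households against 79% of the sample in EAs over 60. That distribution has mean 60, against the stated average of about 50.

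**Conclusion.** The statement is wrong as written for unweighted caregiver-level estimates. The 5:1 maximum ratio of inclusion probabilities follows from the protocol's own figures. The rest depends on an assumed size distribution with mean about 50 and SD 10-20: EAs over 60 households hold about 19-44% of households but 24-56% of the sample, and prevalence is biased by about 0.5-1.3 points if the outcome runs from 20% to 40% across EA sizes. With no gradient there is no bias. Listenership, radio reach and prevalence are affected; the DID much less so if EA sizes are similarly distributed in the two arms. If ward closing is used without a random, recorded order, the inclusion probabilities may not be recoverable. The point deserves correction because the remedy is cheap and part of it must be in place before fieldwork, but it does not threaten the main comparison.

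**What to change.** Choose one of two designs.

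1. **Equal-probability draw of EAs, keeping take-all.** Household inclusion is then equal before any ward rule. The cost is more EAs for the same yield: about 300 (290-303 under the distributions above) against about 260-290 under PPS.

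2. **Keep PPS and weight.** Weight each caregiver by the inverse of the EA's overall inclusion probability: the probability of selection in the first or second PPS draw, times the share of drawn EAs opened in that ward. Apply the ward subsampling fraction as a further factor to cohort and endline estimates only, not to baseline listenership. Use the weights for listenership and prevalence estimates, and as a sensitivity analysis of the DID. The variance cost is the Kish factor of 1.04-1.11, a loss of about 4-10% of effective sample size (1 − 1/1.04 to 1 − 1/1.11).

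Under either design, open EAs within each ward in a pre-set random order and record which are opened, at some cost in field routing. If a ward is closed early or subsampled, the equal-probability design also needs the corresponding factor. Reword the sampling section so that representativeness is claimed only for estimates weighted by inclusion probability, or for a design shown to be self-weighting.

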Data sources / methods	
Enumeration/enrolment questionnaire:
 
 ▪ Background / SES ▪ Listenership survey (dose) ▪ Basic caregiver knowledge/attitudes/practices (awareness of developmental needs) 
Administered by data collectors at enumeration and endline in community
	
Caregiver questionnaire:
 
 ▪ In-depth caregiver capacity and psychosocial status (stress, anxiety, depression, IQ) ▪ Parenting attitudes (discipline), practices (borrow RISE, MICS, other) ▪ CHW exposure ▪ Video exposure and listenership at endline 
Administered by research associates in home (by appointment after enumeration)
	
CHW questionnaire:
 
 ▪ Background/SES ▪ CHW practices, attitudes and capacity (IQ) ▪ Psychosocial status (anxiety, depression) ▪ Listenership survey ▪ Use of and attitudes toward videos at endline 
CHW observation checklists:
 
 ▪ Checklist for home (2 visits at baseline; 2 visits at endline) ▪ Checklist for clinic (2 assessments at baseline and 2 at endline) 
Completed by research associates in home and clinic
 
FGDs/IDIs using qualitative guides

Intervention Description

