The outcome parameters used for sample size calculations for objectives 1 and 2 are estimated from the Malezi I program evaluation baseline data (before introduction of CCD program), comparable to what we would expect in the MR intervention group, who have not been exposed to any CCD intervention. From 24-29% of caregivers reported having a local or shop toy in the home, 22% reported singing to the child in the past month, and 7-13% reported reading or writing with the child in the past week.

Objective 1: To determine caregiver radio listenership patterns at baseline, and exposures to the ECD radio messaging nine months' post-intervention, and effect of radio exposure on caregiver ECD perceptions, knowledge and reported parenting practices, using pre-post surveys in a cohort of caregivers of children 0-24 months of age at baseline, in study communities from each intervention arm.

A sample size of 593 enrolled in the MR intervention group will provide 80% to detect a 5% or greater change from baseline (10%) to endline (15%) in the MR intervention group, taking into account 15% LTFU, design effect of 1.2, and estimated correlation of 0.4 between respondents at baseline and endline (Table 3). This sample size will provide even greater power to detect a 10% difference if baseline estimates are higher than 10%.

Table 3. Sample size estimation* parameters, MR group, caregiver cohort, pre-post

Arm	Prevalence of key outcome			Power	Sample size	Adjusted Sample size (15% LTFU, DE 1.2)
	Baseline	Endline	Expected Change			
MR (Malezi radio)	10%	15%	5%	80%	420	593
	20%	30%	10%	99%	419	592
	25%	35%	10%	98%	411	580

*STATA 14 paired proportions large-sample McNemar's test at 5% level significance.

Objective 2: To determine whether the Malezi II full intervention (MRV-CCD) significantly increases caregiver's knowledge and parenting behaviors/practices when compared to radio messaging alone, using a pre-post quasi-experimental evaluation design in a cohort of caregivers of children 0-24 months of age at baseline, in MRV-CCD and MR communities.

The change between baseline and endline in the Malezi I evaluation for the above-mentioned indicators ranged from 10-30% after introduction of the Malezi I CCD program. With the introduction of radio messaging only, we estimate a 5-10% effect size, and about a 20-30% effect size in the full intervention (MRV-CCD) group (Table 4).

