require clarification or re-training of research associates. All interviews should be done in a private room or location; the caregiver's young child(ren) may be present.

The enumeration listing will require about 5-10 minutes to complete, and will include documentation of children in the household 0-24 months, by date of birth, age, and first name. Household ID number and location coordinates, and other details describing location will also be documented.

The screening form will require about 5-10 minutes to complete, and will include documentation of all inclusion and exclusion criteria, household identification details, and confirmation by the data collector that the respondent provided informed verbal consent for participation.

The locator form will require about 5-10 minute to complete, and will include documentation of the household's location and description, and the caregiver's contact details (phone numbers), and preferred times/days to be re-contacted for stage II participation.

The listenership survey will require 15-30 minutes to complete, and will include questions about the household's socio-economic status (assets, wall/roof materials) and the informant's demographics (age, sex, position in household in relation to the child, employment, followed by questions about their exposure to radio communication, and recall of health education messages (including ECD-related) with respect to content, and source. Most study questions on this survey instrument have been used previously in Tanzania by this team or other researchers.

The caregiver survey will require about 60 minutes, and include questions as follows:

- Child characteristics (registration status, feeding)
- Baseline exposure to CHW home visits, child health, health care seeking
- ECD and early stimulation knowledge and practices (including discipline) – excerpted from UNICEF's MICS6* tool (42,43) and Stellenbosch University's RISE tool designed for standardized ECD/CCD program monitoring and evaluation
- Depression, anxiety, parenting stress, and cognitive ability (non-verbal IQ)
- Household environment (safety, play, shared caretaking)
- Exposure to Malezi program videos and radio messaging (at endline only)

Outcomes and Measures: Caregiver Cohort

Primary outcomes of caregiving behaviors/practices are:

- Caregiver knowledge: Reported knowledge about ECD and perceived importance of early stimulation

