- Caregiver behaviors/practices: Reported responsiveness and discipline practices
- Child stimulation practices: Reported early stimulation practices, such as play, communication, teaching, access to education materials

Secondary outcomes are:

- Child environment: Reported risk and safety measures/practices, observed risks in the household environment
- Acceptability of videos: Caregiver perceptions of ECD videos (e.g., culturally acceptable, useful)

Other measures included as potential confounders or covariates are:

- Caregiver cognition: Evidence suggests that maternal intelligence may moderate the intervention effects (44).
- Parenting stress: Parenting stress, parent-child interactions, perception of child behaviors. There is literature to suggest that parenting stress is prevalent in Africa (45) and is strongly associated with child neglect and lower quality parenting environments (46).
- Caregiver depression: Evidence suggests that depression may reduce the quality of caregiving (14).

The following standardized assessments are included:

IQ - Ravens Standard Progressive Matrix (Ravens): Maternal cognition will be measured using the Raven's Standard Progressive Matrices (often referred to simply as Raven's Matrices) (47). It is the most common test administered to groups ranging from 5-year-olds to the elderly and has been used widely in Sub-Saharan Africa (48). It is a non-verbal assessment, making it culturally sensitive, and takes between 12-15 minutes to administer, dependent on caregiver capacity. It is used to measure abstract reasoning, with the score being regarded as a non-verbal estimate of intelligence.

The measure includes 60 questions, and is presented as a series of 2-dimensional pattern-matching matrices in which 1 small section is missing. Participants are asked to choose from 6 options the one that best fits the missing section. The items become progressively more difficult, and the assessment is stopped when the participant gives 3 consecutive incorrect answers.

The raw scores from the Ravens assessment will be calculated by totaling the number of correct answers given. These continuous raw scores will be used as an indication of general cognition given that tables establishing norms for the Tanzanian adult population are not available. Raw scores will be tested for normal distribution, and a midpoint continuous score can be used as a cut-off for low and high cognition within the group.

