Caregiver stress and the quality of the parent-child relationship - Parenting Stress Index (PSI-36): The PSI is a widely used robust measure of three parenting related domains: Parental distress, parent-child relationship dysfunction (e.g. quality of relationship), and the extent to which the caregiver perceives the child is difficult (49). The scale is composed of 36 statements (12 per sub-scale domain) which are scored 1 (strongly disagree) to 5 (strongly agree), and can be summed to reflect the total score for each domain. A defensive responding score can also be calculated to determine social desirability biases.

To determine parenting stress, items are scored into each of the 3 subscales, with each subscale score ranging from 12-60. The PSI-36 Total Stress Score is a composite score of the three subscales (scores range 36-180) with higher scores indicating higher parental stress (50).

Caregiver mental health, depression - 9-item depression/anxiety scales, PHQ-9 and GAD-7: The 9-item Patient Health Questionnaire tool has been widely used in resource limited settings, and recently validated in a Tanzanian primary care population, showing 78% sensitivity and 87% specificity in detecting depression when compared to a gold-standard psychiatric assessment (51). The items are scored on a 4-point scale, from 0-3, and a cut-off score of 9 was determined to be optimal in classifying depressive symptoms, though a continuous score could also be used.

The General Anxiety Scale of the Patient Health Questionnaire, measures the seven criteria of anxiety in the Diagnostic and Statistical Manual of Mental Disorders (52). These 7 items can establish provisional anxiety diagnosis and assess symptom severity. A systematic review and meta-analysis of both the PHQ9 and GAD7 (53) found that the GAD-7 has good operating characteristics for detecting generalized anxiety, panic, social anxiety and post-traumatic stress disorder. The GAD-7 has been used in LMIC settings (54,55), with HIV infected populations (56,57) and in South Africa (58).

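### All caregiver primary outcomes are self-reported, including materials visible in the home, so any extra rise in over-claiming in MRV-CCD passes straight into the DID; the study's own baseline toy also inflates the endline toy/book item

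*Protocol*

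**What the plan says.** The primary outcomes under Outcomes and Measures: Caregiver Cohort are "Caregiver knowledge: Reported knowledge about ECD and perceived importance of early stimulation", "Caregiver behaviors/practices: Reported responsiveness and discipline practices" and "Child stimulation practices: Reported early stimulation practices, such as play, communication, teaching, access to education materials". Among the caregiver outcomes, direct observation appears only in a secondary one, as "observed risks in the household environment". Table 1 has research associates give the caregiver questionnaire in the home.

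Sample Size Calculations draws on Malezi I baseline figures that include a physical object taken by report: "From 24-29% of caregivers reported having a local or shop toy in the home". The MR group is expected to resemble those figures.

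Table 2 gives both arms the same radio messaging. For MRV-CCD it adds an estimated 2-4 group sessions at the clinic and 3-6 individual sessions at home over nine months. Intervention Description says the CCD programme has run in the MRV-CCD areas since 2016, and that standard-of-care CHW visits take place in all districts.

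Data Analysis defines the DID as the endline difference between groups less the baseline difference.

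On social desirability, the description of the Parenting Stress Index says: "A defensive responding score can also be calculated to determine social desirability biases". No use of that score is tied to the primary outcomes.

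Risks, Benefits and Compensation offers each cohort caregiver a soft locally made toy (a doll, an animal or a book) at the baseline and endline assessments.

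**The concern.** A DID removes over-reporting that stays the same within each arm. It does not remove over-reporting that grows more in one arm than in the other. After baseline, MRV-CCD caregivers are counselled in person, with new videos, on what a caregiver should have and do. MR caregivers get the radio messages without that counselling. Arms are whole districts, so caregiver and interviewer both know the arm. Research associates also attend CHW home visits to MRV-CCD cohort households, so in that arm some caregivers will have met them beside the CHW who counsels them.

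The protocol recognises the gap between report and observation for CHWs: it expects observed counselling skill to be lower than self-reported behaviour and uses checklists. The caregiver primary outcomes have no comparable check, even for objects that can be seen.

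The baseline gift is a second problem for the same items. A household that owned no toy or book at baseline may own one at endline because the study supplied it. What the research associate records in the home, and whether gifts are told apart, must be settled before data collection. It cannot be recovered in the analysis.

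**Working it through.** **The plan's own figure.** 430 x 1.2 / 0.85 = 607.06, the stated 607 per group. Working back, 607 enrolled is worth about 430 after 15% loss and a design effect of 1.2, so n=430 is used below. A large-sample McNemar calculation with r=0.4 gives 81.0% power for MR 10% to 15%, as stated in Table 4.

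**Inputs from the Protocol.** Toy ownership before CCD: 24-29%, taken as 25% for MR. Malezi I rise: 10-30 points, so an established CCD area might start at 25+10=35% to 25+30=55%. Correlation 0.4, stated for Objective 1 only. Significance level 5%, taken as two-sided.

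**Assumptions (not in the documents).** True change of 5 points in both arms, so the true DID is 0. A fraction f = 5-10% of MRV-CCD non-owners claim the item at endline only. No growth in over-claiming in MR.

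**Bias.** Reported DID = true DID + (rise in over-claiming in MRV-CCD - rise in MR). Here the bias is f x (1 - true MRV-CCD endline prevalence).

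**Standard error.** For an arm going from p to q, v = p(1-p) + q(1-q) - 2r·sqrt[p(1-p)q(1-q)], and SE = sqrt[(v_MR + v_MRV)/430].
- MR 25 to 30%: v = 0.3975 - 0.8 x 0.1984 = 0.2388.
- MRV-CCD 35 to 40%: v = 0.4675 - 0.8 x 0.2337 = 0.2806.
- SE = sqrt(0.5194/430) = 0.0347.

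Rejection probability = Φ(bias/SE - 1.96) + Φ(-bias/SE - 1.96):

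| MRV-CCD true change | Bias, f=5% to 10% | SE (r=0.4) | False significance, r=0.4 | r=0 |
|---|---|---|---|---|
| 35 to 40% | 3.0 to 6.0 points | 3.5 points | 14 to 41% | 10 to 27% |
| 45 to 50% | 2.5 to 5.0 | 3.5 | 11 to 29% | 9 to 19% |
| 55 to 60% | 2.0 to 4.0 | 3.5 | 9 to 21% | 7 to 14% |

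**If MR also over-claims.** Let MR non-owners over-claim at half the rate, f/2 x 0.70 = 1.75 to 3.5 points. The net bias falls to between 0.25 point (2.0 - 1.75) and 2.5 points (6.0 - 3.5), and false significance at r=0.4 to about 5-11%.

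**If over-claiming is constant over time.** With f the same at both rounds, the bias is f x [(1 - endline) - (1 - baseline)] = -0.05f, or -0.25 to -0.5 point. It nearly cancels.

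**The gift.** Suppose it makes a fraction g of endline non-owners into owners (g assumed). The MR pre-post change rises by 0.70g: 7 points at g=10% and 35 at g=50%, against an expected radio effect of 5-10 points. MR has more non-owners, so the DID shifts by g x (0.60 - 0.70) = -1 to -5 points when MRV-CCD is at 40%, and by g x (0.40 - 0.70) = -3 to -15 points at 60%. The gift therefore inflates Objective 1 on this item and can mask a DID in Objective 2.

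**The case against.** The case on the other side has weight.

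- No over-claim rate is given anywhere, so every figure above is a scenario. A reader might take the Table 4 prevalences (MR 10 to 15%, MRV-CCD 25% at baseline, rising to 30% under no true DID) and infer a bias of 3.5-7 points with 22-66% false significance. That arithmetic reproduces at r=0.4 (SE 2.94 points), but the 10% baseline fits reading or writing with the child (7-13%), which cannot be sighted. Toys start at 24-29%.
- MR caregivers hear many messages, aired daily for nine months, and may learn the desired answers too. CCD since 2016 puts some coached answering into the MRV-CCD baseline, where it is subtracted. Both points stand and reduce the likely size.
- Sighting is imperfect. Programme toys are mostly home-made or household objects, so whether one counts as a toy still rests partly on the caregiver's word. The rater knows the arm. Scoring only sighted items would also weaken comparability with MICS. These points tell against replacing the reported primary outcome, but not against recording the sighted version beside it.
- The survey items are not shown, and the household environment section may already cover some play materials. Even so, the stated definition of the primary outcome is by report, and how the defensive responding score is analysed could properly sit in an analysis plan.

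**Conclusion.** The point holds as a design weakness of unknown size. The primary outcomes rest on report even where the interviewer could look, and the arms differ after baseline in face-to-face counselling, so a net rise in over-claiming in MRV-CCD enters the DID in full. Under the stated assumptions (5-10% of non-owners, MRV-CCD only, endline only, n=430, r=0.4, toy-like prevalences) the bias is about 2-6 points, against a planned DID of 15, with false significance of about 9-41%. It is smaller if r is lower or if MR caregivers also over-claim.

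A reader might infer that a positive DID on stimulation could not be told from learned answers at all. The documents do not support that: the bias is possible but not shown, part of it is already in the baseline, and it would have to be large to produce the whole planned effect. Nor do they support making an unblinded seen/not-seen rating the primary outcome.

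The gift problem does not depend on over-claiming. It depends only on the toy or book being kept and counted at endline.

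**What to change.** 1. At baseline and endline, have the research associate ask to see toys, books and play materials, record each as seen or not seen, and mark any study gift.
2. Exclude study gifts from the endline toy/book item, in the reported version as well as the sighted one.
3. Keep the reported outcome primary. Prespecify the DID on the sighted, gift-excluded items as a supportive analysis, and state that the conclusion on these items depends on its agreement with the reported version. The arm-by-time difference in reported minus sighted ownership is a direct measure of differential reporting and should be shown with its confidence interval.
4. Compute the PSI defensive responding score at both rounds and report it by arm and time, beside the outcomes that cannot be sighted.

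Cost: an estimated one or two more minutes on a home survey of about 60 minutes, with no extra staff. Some items in use elsewhere will be scored not seen. Sighting cannot verify knowledge, responsiveness, discipline or activities such as singing and reading, so for those the defensive responding score is the only check, and an indirect one.
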